5.5.2.1. Myeloid Growth Factors

Myeloid growth factors (including pegfilgrastim) should not be given within 24 hours prior to any dose of LV. In Parts C and D, myeloid growth factor use is allowed per ASCO guidelines. However, for patients enrolled in Part C and D, long-acting myeloid growth factors (such as pegfilgrastim) may not be appropriate because LV is given either weekly or on Days 1 and 8 every 21 days. Long-acting myeloid growth factors should only be given when there is sufficient time for the growth factors to have cleared and for growth stimulatory activity to have ceased.

5.5.3. Prohibited Concomitant Therapy

Patients are prohibited from receiving the following therapies during the screening and treatment phase of this trial:

- Antineoplastic systemic chemotherapy or biological therapy
- Immunotherapy not specified in this protocol
- Chemotherapy not specified in this protocol
- Investigational agents other than pembrolizumab and LV
- Radiation therapy with the following exceptions:

- Radiation therapy to a symptomatic, non-target solitary lesion may be considered on an exceptional case-by-case basis after consultation with sponsor. The patient must have clear measurable disease outside the radiated field.
- Palliative radiation therapy may be allowed under the criteria outlined in Section 5.5.2.
- Live vaccines within 30 days prior to the first dose of study treatment and while
 participating in the trial. Examples of live vaccines include, but are not limited to, the
 following: measles, mumps, rubella, chicken pox, yellow fever, rabies, Bacillus
 Calmette-Guerin, and typhoid (oral) vaccine. Seasonal influenza vaccines for injection
 are generally killed virus vaccines and are allowed. However, intranasal influenza
 vaccines (e.g., Flu Mist[®]) are live attenuated vaccines, and are not allowed.
- Systemic glucocorticoids for any purpose other than to modulate symptoms from an
 event of clinical interest of suspected immunologic etiology. The use of physiologic
 doses of corticosteroids may be approved after consultation with the sponsor.
 - Note: Inhaled steroids are allowed for management of asthma.

Patients who, in the assessment by the investigator, require the use of any of the aforementioned treatments for clinical management should be removed from the trial. Patients may receive other medications that the investigator deems to be medically necessary.

Patients in Part C dose escalation cohorts should not receive prophylactic G-CSF in Cycle 1.

The Exclusion Criteria describe other medications that are prohibited in this trial.

There are no prohibited therapies during the post-treatment follow-up phase.

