4.4.1. Discontinuation of Study Treatment

A patient's study treatment may be discontinued for any of the following reasons:

- Progressive disease (PD)
- AE
- Pregnancy
- Investigator decision
- Patient decision, non-AE
- Study termination by sponsor
- Other, non-AE

Patients who discontinue from study treatment will remain on study for follow-up unless they withdraw consent.

Discontinuation of pembrolizumab may be considered for patients who have attained a confirmed CR that has been treated for at least 8 cycles (24 weeks) and had at least 2 treatments with pembrolizumab beyond the date when the initial CR was declared.

Patients who discontinue pembrolizumab may continue to receive LV with medical monitor approval (see Section 5.2.5). Similarly, patients that discontinue LV may continue to receive pembrolizumab with medical monitor approval (see Section 5.3.5).

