4.4.2. Patient Withdrawal from Study

Any patient may be discontinued from the study for any of the following reasons:

- Patient withdrawal of consent
- Study termination by sponsor
- Completion of protocol specified safety follow-up (see Section •)
- Lost to follow-up
- Death
- Other

TREATMENTS

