6.4. Response Assessments

Time points for radiographic exams should be calendar based and do not depend on cycle visits (see Section 7.2). Imaging should be conducted on the following schedule until disease progression, unacceptable toxicity, start of a new cancer therapy, consent withdrawal, investigator decision, study termination by the sponsor, or death, whichever comes first:

Every 6 weeks (±3 days) for 12 months after the first dose of LV and pembrolizumab

Every 12 weeks (±7 days) thereafter

No additional scans or response assessments are required after the safety follow-up period, however additional scans or response assessments may be performed as part of the patient's standard of care at any time.

6.5. End of Treatment Visit (30 to 37 days after last dose of study drug)

End of treatment (EOT) visits should occur 30 to 37 days after the last dose of study drug unless delayed due to an AE. Note: The time to EOT visit may be longer than 37 days, but in no case should it be <30 days. However, EOT evaluations must be performed before initiation of a new therapy. If EOT evaluations are completed before 30 days after the last study treatment, the patient will be contacted 30 to 37 days following the last treatment to assess for AEs.

- ECOG Performance status (see Appendix F)
- Physical examination (see Section 7.5.4)
- Pregnancy test (for patients of childbearing potential; performed locally)
- Serum chemistry panel (detailed in Section 7.5.3)
- CBC with differential (detailed in Section 7.5.3)
- HbA1c (performed locally)
- CT of chest, abdomen, and pelvis (and neck if clinically indicated) (MRI may also be acceptable; see Section 7.1) (not required if conducted within 4 weeks prior to EOT)
- Collection of concomitant medication information
- Collection of AEs

If patients are discontinuing treatment due to PD, and a biopsy was done as standard of care at disease progression, a tumor sample is requested, if available.

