6.6. Follow-up

Patients who discontinue study treatment in the absence of disease progression will remain on the study for follow-up until withdrawal of consent, initiation of a new anticancer therapy, death, or study closure, whichever occurs first. The first follow-up visit will occur 6 weeks (±1 week) from the most recent prior radiographic response evaluation. Subsequent follow-up visits will be scheduled for 6 weeks (±1 week) from the previous follow-up visit. After 1 year on study, the frequency of follow-up visits will be reduced to every 12 weeks (±1 week).

The following assessments will be conducted at follow-up visits until progression or initiation of a new anticancer treatment through the end of the safety follow-up period:

- Physical examination (see Section 7.5.4)
- CT of chest, abdomen, and pelvis (and neck if clinically indicated) (MRI may also be
 acceptable; see Section 7.1); after a year of follow-up, reduce frequency to institution's
 standard of care until progression or initiation of a new anticancer therapy.
- Concomitant medication information and AEs to be collected if serious and considered to be study treatment-related.

Safety Follow-Up

Patients discontinuing treatment will be followed for the protocol required safety follow-up period, unless additional safety concerns warrant further follow-up:

- 30 days post treatment for LV and
- 90 days post treatment for pembrolizumab.

No additional follow-up is required after the safety follow-up period.

After disease progression or initiation of a new anticancer treatment, survival follow-up will be conducted, every 12 weeks (±2 weeks) starting from the last radiographic scan demonstrating disease progression or from initiation of the new anticancer treatment until completion of the safety follow-up period, death, or study closure, whichever comes first. Follow-up may be conducted with clinic visits or telephone calls. No further response assessments will be conducted.

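### Section 5.5.3 takes patients who need a prohibited therapy out of the trial, which conflicts with the follow-up required by Sections 4.4.1, 6.6 and 7.5.1.3

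*Protocol*

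**What the plan says.** Section 5.5.3 lists therapies barred during screening and treatment: other anticancer drugs, investigational agents, most radiotherapy, live vaccines, and systemic glucocorticoids outside narrow exceptions. It then says that patients who, in the investigator's assessment, "require the use of any of the aforementioned treatments for clinical management should be removed from the trial". The section ends: "There are no prohibited therapies during the post-treatment follow-up phase".

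Other sections govern what happens once treatment stops:

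- Section 4.4.1: "Patients who discontinue from study treatment will remain on study for follow-up unless they withdraw consent".
- Section 4.4.2 lists the reasons for leaving the study. They include "Completion of protocol specified safety follow-up" and a catch-all, but not the need for a prohibited therapy.
- Section 6.5: "End of treatment (EOT) visits should occur 30 to 37 days after the last dose of study drug unless delayed due to an AE". A CT is part of that visit but is "not required if conducted within 4 weeks prior to EOT".
- Section 6.6: "The first follow-up visit will occur 6 weeks (±1 week) from the most recent prior radiographic response evaluation". Safety follow-up is 30 days for LV and "90 days post treatment for pembrolizumab". Survival follow-up continues within that period even after new anticancer therapy.
- Section 7.5.1.3: SAEs are reported to the EOT visit or 90 days after the last study treatment, whichever is later.
- Figures 1 and 2, footnote a: a first objective response calls for a further scan at least 4 weeks later.

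**The concern.** Section 4.4 separates stopping study treatment from leaving the study, and 5.5.3 ignores that distinction. Other parts of the protocol observe it: Table 8, for example, specifies permanent discontinuation of study drug after a severe pembrolizumab infusion reaction. Sites working from 5.5.3 and sites working from 4.4.1 could therefore handle the same event differently.

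What is at stake is mainly safety information. Safety is a primary objective, and Section 5.3.5.1 warns that immune-related events can appear months after the last pembrolizumab dose, so the later part of the 90-day window matters. The patients concerned are those who needed additional treatment, and they are unlikely to be a random subset. The steroid trigger is plausible: Section 5.7 foresees steroids given for other conditions, while the 5.5.3 exemption is limited to suspected immune events and approved physiologic doses, with inhaled steroids allowed for asthma.

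**Working it through.** The plan states no figure on this point, so there is nothing to reproduce. The check is a subtraction using the protocol's own windows.

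**Inputs**

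- Pembrolizumab safety follow-up: 90 days (6.6).
- LV safety follow-up: 30 days (6.6).
- On-time EOT: day E = 30 to 37 after the last dose of any study drug (6.5).
- SAE window: 90 days from the last study treatment (7.5.1.3).
- g = days from the last pembrolizumab dose to the last dose of any study drug. Pembrolizumab is given on Day 1, so g = 0 if both were last given that day, 7 if LV was last given on Day 8 of the same cycle, and 14 if on Day 15.

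**Days lost if the patient leaves at an on-time EOT visit**

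Pembrolizumab window lost = 90 − (E + g), not below 0.

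| Situation | g | E = 37 | E = 30 | Lost |
|---|---|---|---|---|
| Both drugs last given the same day | 0 | 90 − 37 = 53 | 90 − 30 = 60 | 53–60 days (59–67%) |
| Part D, last LV on Day 8 | 7 | 90 − 44 = 46 | 90 − 37 = 53 | 46–53 days |
| Part C, last LV on Day 15 | 14 | 90 − 51 = 39 | 90 − 44 = 46 | 39–46 days |
| Pembrolizumab stopped well before LV | ≥53 (E = 37) or ≥60 (E = 30) | 0 | 0 | none |

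SAE window lost = 90 − E = 53 to 60 days in every part, because that window and the EOT visit both run from the last study treatment.

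LV window lost = 30 − E, which is 0 or below, so nothing is lost. A patient removed before EOT loses more, up to the full 30 and 90 days and the EOT assessments.

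**Which endpoints can be touched**

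- *Trigger is new anticancer therapy.* Sections 6.4 and 6.6 already end imaging at that point. SAP 6.6.1.2 and 6.6.1.4 censor DOR and PFS at the last assessment before the new therapy, and SAP Appendix E ignores later responses. Removal costs safety, SAE and short survival follow-up, but no protocol scans.
- *Trigger is not new anticancer therapy*, mainly non-exempt systemic steroids, live vaccines, or radiotherapy not counted as anticancer therapy. Imaging would otherwise continue through safety follow-up. SAP 6.6.1.2 censors a removed patient at the last assessment, and SAP 6.6.1.1 counts a response without a confirmation scan as a non-response.

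The radiotherapy group may be small: SAP 8.2 says palliative radiotherapy to a non-progressing non-target lesion does count as new antitumor treatment, although SAP 6.6.1.2 still exempts it.

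**Illustration of the confirmation scan (nominal dates)**

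Last dose on Cycle 2 Day 1 is study day 22. The week 6 scan is on study day 43, which is 43 − 22 = 21 days after last dose. If it shows a first response, EOT on days 30 to 37 falls 9 to 16 days later, so the EOT CT is not required and would be too early to confirm. The footnote a scan can be done from day 21 + 28 = 49, and the 6.6 scan is due on day 21 + 42 = 63. Both fall after EOT and inside the 90 days, and removal at EOT forfeits both. This shows the mechanism only; it says nothing about how often it happens.

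**The case against.** The strongest reply is that the protocol already settles the matter. The prohibition covers only screening and treatment, and the last line of 5.5.3 presupposes that patients move into follow-up. Section 4.4.1 is explicit, Section 6.6 makes no exception, and Section 7.5.1.3 ties SAE reporting to last treatment rather than study status, with treatment-related SAEs reportable even later. For a patient still in screening, removal from the trial is the natural phrase. All of this stands as evidence of intent, and it is why the point is minor. It does not change the instruction as written, which a site could follow in good faith.

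It can also be said that a site reading 5.5.3 literally would not wait for an EOT visit. That is fair: the 53 to 60 days describe one scenario, and earlier removal loses more.

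A reader might infer several stronger things that the documents do not support:

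- That the protocol intends to drop these patients from follow-up. The closing line of 5.5.3 points the other way.
- That 53 to 60 days of pembrolizumab follow-up is the loss in all parts. It holds only when both drugs were last given on the same day and EOT is on time.
- That scans are lost whatever the trigger. Imaging already ends at new anticancer therapy.
- That ORR would shift by a stated amount. One lost responder changes a rate by 100/n points, but nothing shows that any such patient exists.
- That confirmation of a late response rests on Section 6.6 alone. Footnote a to Figures 1 and 2 requires a scan separately, although removal would forfeit that one too.

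**Conclusion.** The conflict is real and is in the current text: for treated patients, 5.5.3 as worded cannot be reconciled with 4.4.1, 6.6 and 7.5.1.3. The size depends on when the patient leaves and on which drug was given last, as tabulated above. The day counts assume that a site applies the wording literally and that the patient leaves at an EOT visit on days 30 to 37. An EOT visit delayed by an AE shortens the loss, and removal before day 30 lengthens it.

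The documents give no removal rate, so no number of patients, missed events, or effect on ORR, PFS, DOR or OS is claimed. All analyses are descriptive. Severity is minor: a wording conflict in a stated rule, with a workable reading, that could cost some safety data and lead to uneven handling between sites.

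**What to change.** In Section 5.5.3, replace the instruction to remove the patient with: *should discontinue study treatment (or not start it, if still in screening); treated patients remain on study for EOT, response, safety and survival follow-up per Sections 4.4.1, 6.5, 6.6 and 7.5.1.3*. With that wording no follow-up days are lost for this reason. The cost is one phrase, with no visits beyond those already required.

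If no patient is still on treatment, a short listing in the clinical study report serves instead: any patients taken off study for this reason, with last dose date, censoring dates, and whether a response was awaiting confirmation. Section 4.4.2 does not name this reason, and the CRF is not among the documents, so the SAP 6.1 disposition summary may not identify them.

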5.6. Management of Adverse Reactions

5.6.1. Management of Infusion Reactions

5.6.1.1. LV

IRRs may occur during the infusion of study treatment. The infusion should be administered at a site properly equipped and staffed to manage anaphylaxis should it occur. Routine premedication should not be administered for the prevention of IRRs prior to the first dose of LV.

All supportive measures consistent with optimal patient care should be given throughout the study according to institutional standards. Supportive measures may include extending the infusion time and/or administering medications for IRRs.

Patients who have experienced a Grade 1 or Grade 2 IRR with LV should be premedicated for subsequent infusions.

Patients who experience a Grade 3 IRR may potentially receive additional treatment with LV at the discretion of the investigator after discussion with the sponsor's medical monitor.

Premedication may include acetaminophen, an antihistamine, and a corticosteroid administered 30–60 minutes prior to each infusion or according to institutional standards.

If anaphylaxis or a Grade 4 IRR occurs, LV administration should be immediately and permanently discontinued.

5.6.1.2. Pembrolizumab

Please refer to the recommendations in Table 8.

5.6.1.3. Infusion Related Reaction of Uncertain Cause

If a patient experiences an IRR after receiving both study treatments and a single cause of the IRR cannot be determined, both sets of guidelines for IRRs must be followed.

5.6.2. Supportive Care Guidelines for Pembrolizumab

Patients should receive appropriate supportive care measures as deemed necessary by the treating investigator. Suggested supportive care measures for the management of AEs with potential immunologic etiology are outlined along with the dose modification guidelines in Section 5.3.5, Table 7. Where appropriate, these guidelines include the use of oral or IV treatment with corticosteroids, as well as additional anti-inflammatory agents if symptoms do not improve with administration of corticosteroids. Note that several courses of steroid tapering may be necessary as symptoms may worsen when the steroid dose is decreased. For each disorder, attempts should be made to rule out other causes such as metastatic disease or bacterial or viral infection, which might require additional supportive care. The treatment guidelines are intended to be applied when the Investigator determines the events to be related to pembrolizumab.

Note: If after the evaluation of the event, it is determined not to be related to pembrolizumab, the investigator does not need to follow the treatment guidance. Refer to Section 5.3.5 for guidelines regarding dose modification and supportive care.

It may be necessary to perform conditional procedures such as bronchoscopy, endoscopy, or skin photography as part of evaluation of the event.

5.7. Management of Hyperglycemia

Investigators should monitor blood glucose levels and are advised to perform additional assessments if any symptoms of hyperglycemia are observed, including a thorough evaluation for infection. In addition, if steroids are used to treat any other condition, blood glucose levels may require additional monitoring. If elevated blood glucose levels are observed, patients should be treated according to local standard of care and referral to endocrinology may be considered.

Patients, especially those with a history of or ongoing diabetes mellitus or hyperglycemia, should be advised to immediately notify their physician if their glucose levels become difficult to control or if they experience symptoms suggestive of hyperglycemia such as frequent urination, increased thirst, blurred vision, fatigue, and headache.

Patients who enter the study with elevated hemoglobin A1c (HbA1c) (≥6.5%) or fasting glucose (≥126 mg/dL or ≥7.0 mmol/L) at screening should receive glucose management prior to or within 1 week of starting study treatment.

In Part A and B, blood glucose should be checked prior to each dosing and dose should be withheld for blood glucose >250 mg/dL or >13.9 mmol/L, testing may be repeated on the same day of dosing. LV dose may be delivered on the same day once the patient's blood glucose has improved to ≤250 mg/dL or ≤13.9 mmol/L and the patient is clinically and metabolically stable.

In Part C, blood glucose may be checked on Day 8 and Day 15 by fingerstick as indicated, particularly in patients at risk for hyperglycemia. Day 8 and 15 dosing with LV should be withheld for blood glucose >250 mg/dL or >13.9 mmol/L. Testing may be repeated on the day of dosing. LV dose may be delivered on the same day once the patient's blood glucose has improved to ≤250 mg/dL or ≤13.9 mmol/L and the patient is clinically and metabolically stable.

In Part D, blood glucose may be checked on Day 8 by fingerstick as indicated, particularly in patients at risk for hyperglycemia. Day 8 dosing with LV should be withheld for blood glucose >250 mg/dL or >13.9 mmol/L. Testing may be repeated on the day of dosing. LV dose may be delivered on the same day once the patient's blood glucose has improved to ≤250 mg/dL or ≤13.9 mmol/L and the patient is clinically and metabolically stable.

5.8. Treatment Compliance

Study drug administration will be performed by study site staff and documented in source documents.

Amendment 11: 19-Oct-2023

Page 63 of 152

STUDY ACTIVITIES

6.1. Schedule of Events

AEs and concomitant medications will be recorded from Day 1 (predose) through the safety reporting period (see Section 7.5.1.3). Any study protocol-related AE (defined in Section 7.5.1.1), as well as any concomitant medications given for treatment of the AE, should be recorded from the time of informed consent. Schedules of events are provided in Appendix A, Appendix B, Appendix C, Appendix D, and Appendix E.

Study activities are listed by visit in this section and descriptions of all study assessments are presented in Section 7.

6.2. Parts A and B (q3wk LV dosing)

6.2.1. Screening Visit (Days –28 to 1)

- Informed consent
- Study eligibility per inclusion/exclusion criteria
- Medical history (See Section 7.1)
- Brain CT or magnetic resonance imaging (MRI)
- Collection of archived tumor specimen, if available
- Biopsy, freshly obtained, submitted for central assessment (see Appendix E)
- Electrocardiogram (ECG) (see Section 7.1.1)
- Serology for hepatitis B surface antigen and antihepatitis B core antibody (detailed in Section 7.5.3)
- PCR for hepatitis C virus (detailed in Section 7.5.3)
- HbA1c and fasting blood glucose (detailed in Section 7.5.3)
 - If HbA1c or fasting glucose is elevated with confirmation upon repeat testing (HbA1c ≥6.5%, fasting glucose ≥126 mg/dL, or ≥7.0 mmol/L), the patient should receive glucose management before Cycle 1 Day 1 or within the first week of Cycle 1
- PT/PTT/aPTT/INR (detailed in Section 7.5.3)
- CT of chest, abdomen, and pelvis (and neck if clinically indicated) (MRI may also be acceptable; see Section 7.1)Thyroid function tests (detailed in Section 7.5.3)
- Collection of concomitant medication information
- Collection of AEs

6.2.2. Baseline Visit (Days –7 to 1)

- Height and weight (see Section 7.1)
- Vital signs (see Section 7.5.2)
- Physical examination (see Section 7.5.4)
- ECOG Performance status (see Appendix F)
- Serum chemistry panel (detailed in Section 7.5.3)
- Complete blood count (CBC) with differential (detailed in Section 7.5.3)

- Pregnancy test for patients of childbearing potential performed within 3 days prior to Cycle 1 Day 1 (performed locally)
- Collection of concomitant medication information
- Collection of AEs

